10. REGULATORY CONSIDERATIONS

10.1. CLINICAL TRIAL MONITORING

The PI will review study data on a quarterly basis and ensure that study documents are monitored at least annually for the duration of the study for data accuracy and completeness.

10.2. RECORDS TO BE KEPT

10.2.1 CASE REPORT FORMS (CRFs)

As used in this protocol, the term case report form (CRF) refers to either a paper form or an electronic data record or both, depending on the data collection method used in this study. A CRF is required and should be completed for each included participant.

The investigator has ultimate responsibility for the accuracy, authenticity, and timely collection and reporting of all clinical, safety, laboratory data entered on the CRFs and any other data collection forms. All CRFs must be signed by the investigator to verify that the data contained on the CRFs is accurate. Any corrections to entries made in the CRFs, source documents must be dated, initialed and explained (if necessary) and should not obscure the original entry.

Usually, source documents are the hospital's or the physician's participant medical chart. In these instances the data collected on the CRFs must match the data in the corresponding charts. A CRF, or part of the CRF, may also serve as a source document.

The PI will maintain a file of human subjects' research project documents including (at a minimum) the following items:

- A copy of the original human subjects research application submitted to the JHM-IRB
- A copy of the JHM IRB approved consent form.
- The original of each consent form signed by each participant enrolled in the research.
- A copy of all correspondence with the IRB and other regulatory institutions as appropriate
- A copy of all data derived from the study (case report forms, computer data, adverse event reports, drug/device accountability records etc.)

10.2.2. RECORD RETENTION

To enable inspections and/or audits from regulatory authorities, the investigator agrees to keep records, including the identity of all participating subjects (i.e. information to link records, e.g., CRFs and hospital records), all original signed informed consent forms, copies of all CRFs, serious adverse event forms, source documents, and detailed records of treatment disposition, and adequate documentation of relevant correspondence (e.g., letters, meeting minutes, telephone calls reports).

The study records will be retained by the investigator for 2 years after either 1) a marketing application is approved or 2) if an application is not approved for the agent, until 2 years after shipment and delivery of the biologic for investigational use is discontinued and the FDA so notified" [21 CFR 312.61(c)].

10.2.3. CLINICAL PHOTOGRAPHS

Photographs of cellular injection sites both before injection and after will be retained as scientific data. No identifying photographs will be taken. For example, no photographs of the face will be taken. All photos will be de-identified and will be maintained in a password protected areas.

APPENDIX I- Phase One (Single Dose)

Visit/ Study Day:	Screening & Consent	Baseline	Suture removal	Graft Injection	Graft Removal / monitoring	Graft Removal / monitoring	Graft Removal ³ / monitoring	Suture Removal ²	Final evaluation				
	Day -14 Through Day -1	Visit 1 Day 0	Visit 2 Day 15 (±3 days)	Visit 3 Day 30 (±10 days)	Visit 4 Day 42 (±7 days)	Visit 5 Day 70 (±7 days)	Visit 6 Day 98 (±7 days)	Visit 7 Day 126 (±7 days)	Visit 8 Day 154 (±7 days)	Day 182 Visit 9 (±7 days)	Day 196 Visit 10 (±7 days)	Day 273 Visit 11 (±14 days)	
Informed consent	X												
Eligibility review	X	X											
Assessments													
Vital signs			X		X	X	X	X	X	X	X		
History & limited physical	X	X		X									
Medication Review	X												
Clinical Photographs		X		X	X	X	X	X	X	X	X	X	X
Biopsy/graft excision site assessment			X								X	X	
Adverse events/symptom diary review		X	X	X	X	X	X	X	X	X	X	X	X
Optical Coherence Tomography					X	X	X	X	X	X	X		
Laboratory Testing													
HIV 1 Antibody	X												
HIV 2 Antibody	X												
HIV Nucleic acid	X												
HTLV I/II Assay (Abs)	X												
Serum HCG ¹	X ¹												
Urine HCG ¹				X ¹									
Hepatitis B Surface Ag	X												
Hepatitis B, Core antibody	X												
Hepatitis C nucleic acid	X												
Procedures													
Skin biopsy		X											
Suture removal			X								X ²		
Investigational injections				X									
Excise 3 graft sites; dress graft sites ³							X ³	X ³	X ³	X			

- 1- Females of child bearing potential only
- 2- 14 days +/- 2 days after early graft removal OR study day 196 +/- 7 days
- 3- ONLY for the first three participants who exhibit statistically significant thickening based upon three OCT measurements

APPENDIX II- Phase Two (Intermittent Dosing Regimen)

Visit/ Study Day:	Screening & Consent Day -14 Through Day -1	Baseline Visit 1 Day 0	Suture removal Visit 2 Day 15 (±3 days)	Graft Injection Visit 3, 4, 5, 6 Day 30,37,42,59 (±10 days)	Graft Removal / monitoring Visit 7 Day 70 (±7 days)	Graft Removal / monitoring Visit 8 Day 98 (±7 days)	Graft Removal ³ / monitoring Visit 9 Day 126 (±7 days)	Graft Removal ³ / monitoring Visit 10 Day 154 (±7 days)	Graft Removal Day 182 Visit 11 (±7 days)	Suture Removal ² Day 196 Visit 12 (±7 days)	Final evaluation Day 273 Visit 13 (±14 days)
Informed consent	X										
Eligibility review	X	X									
Vital signs			X		X	X	X	X	X		
History & limited physical	X	X		X							
Medication Review	X										
Clinical Photographs		X		X	X	X	X	X	X	X	X
Biopsy/graft excision site assessment			X							X	X
Adverse events/symptom diary review		X	X	X	X	X	X	X	X	X	X
Optical Coherence Tomography					X	X	X	X	X		
HIV 1 Antibody	X										
HIV 2 Antibody	X										
HIV Nucleic acid	X										
HTLV I/II Assay (Abs)	X										
Serum HCG ¹	X ¹										
Urine HCG ¹				X ¹							
Hepatitis B Surface Ag	X										
Hepatitis B, Core antibody	X										
Hepatitis C nucleic acid	X										
Skin biopsy		X									
Suture removal			X							X ²	
Investigational injections				X							
Excise 3 graft sites; dress graft sites ³						X ³	X ³	X ³	X		

[figure not shown]
¹ Females of child bearing potential only

- 2- 14 days +/- 2 days after early graft removal OR study day 196 +/- 7 days
- 3- ONLY for the first three participants who exhibit statistically significant thickening based upon three OCT measurements

APPENDIX II- PHOTOGRAPHY SOP

The study PI or other IRB approved study member will be performing photography in the clinic dark room which is adjacent to patient exam room. Nikon D300s digital handheld including a cross-polarized lens (Canfield, TF X-Polarizer Filter Kit).

- 1) Ensure patient is gowned or in tank top to ensure clothing is out of the field.
- 2) Use black backdrop in dark room.
- 3) Position the subject standing facing the photographer approximately 1 foot in front of the black backdrop.
- 4) Hold constant flash output and camera-to-arm distance (approximately >5 feet)
- 5) Ask subject to stand erect, to extend arm 90 degrees from trunk laterally, and to gently place their hand on the vertically placed chain rope.
- 6) Saved photos should have derm study number, subject number, subject initial, and other pertinent body site info in file name.
- 7) All photos will be saved on a password protected computer.

APPENDIX III- BASELINE BIOPSY SPECIMEN PREPARATION AND HANDLING

At Johns Hopkins Hospital, two skin biopsies will be taken to yield non-volar skin and volar skin.

- 1) The chosen biopsy sites will be cleaned as per Departmental Standard of care for skin biopsies which includes alcohol swabs.
- 2) Local anesthesia will be administered consisting of 1% lidocaine with epinephrine as per standard of care.
- 3) After allowing time for anesthesia to take effect, the punch biopsies 2-6mm in diameter by 2mm deep will be obtained from the preselected sites.
- 4) One stitch will be put in each biopsy site to aid healing.
- 5) The biopsies will be kept separate and placed into labeled sterile 50 ml tubes containing Dulbecco's Phosphate Buffered Saline (DPBS) containing penicillin (100 units/ml), streptomycin (100 ug/ml) and Amphotericin B (0.25 ug/ml) prior to room temperature transport to the Cell Therapy Laboratory. Labeling of tubes will include the subject initials, unique participant ID, the date, the biopsy sites, and the identity (volar vs nonvolar).
- 6) The biopsies will be directly hand delivered to the Cell Therapy Lab and received by lab staff as per CTL protocol.
- 7) Upon receipt, each biopsy may be processed immediately or the tubes may be placed into a 2-8°C refrigerator for up to 24 hours.
- 8) Following this, fibroblast isolation will begin as per CTL protocol.

APPENDIX V- CELL ADMINISTRATION SHEET

NA_00068684
AUTOLOGOUS FIBROBLAST ADMINISTRATION RECORD

PARTICIPANT NAME: _____

DATE OF ADMINISTRATION: _____

#	INJECTION LOCATION	VIAL IDENTIFICATION NUMBER	TIME INJECTION BEGUN	TIME INJECTION COMPLETED	CELL DOSE
1					
2					
3					

ADMINISTERED BY: _____

DATE: _____

TIME: _____

APPENDIX VI- INJECTION SITE PATIENT DIARY

NA_00068684 INJECTION SITE PATIENT DIARY

DATE: _____

PATIENT NAME: _____

DATE	SITE LOCATION	SITE COLOR	SITE SIZE (e.g. Dime, nickel, etc.)	SITE DISCOMFORT (Use table for code)	PHYSICAL SYMPTOMS (i.e. Fever, headache, skin rash, etc)	COMMENTS
	1					
	2					
	3					
	1					
	2					
	3					
	1					
	2					
	3					
	1					
	2					
	3					
	1					
	2					
	3					

REACTION COLOR CODES		DISCOMFORT CODES		SITE DIAGRAM	
A	NO REACTOIN	1	NO DISCOMFORT		
B	LIGHT PINK	2	SWELLING		
C	DARK PINK	3	ITCHING		
D	RED	4	TENDERNESS		
E	PURPLE	5	WARMTH		
F	OTHER	6	OTHER		

APPENDIX VII- BASELINE BIOPSY SPECIMEN PREPARATION AND HANDLING

At Johns Hopkins Hospital, we will perform final biopsies to remove the skin from the 3 injection sites.

- 1) The chosen biopsy sites will be cleaned as per Departmental Standard of care for skin biopsies which includes alcohol swabs.
- 2) Local anesthesia will be administered consisting of 1% lidocaine with epinephrine as per standard of care.
- 3) After allowing time for anesthesia to take effect, the punch biopsies 3-6mm in diameter by 2mm deep will be obtained from the injected sites.
- 4) One stitch will be put in each biopsy site to aid healing.
- 5) The biopsies will be kept bisected with $\frac{1}{2}$ placed in RNA-later and $\frac{1}{2}$ placed in paraformaldehyde. Labeling of tubes will include the subject initials, unique participant ID, the date, the injection #, and the identity (vehicle, volar or nonvolar).
- 6) The biopsies will be directly hand delivered to the [name] lab.
- 7) Upon receipt, each biopsy may be processed immediately or the tubes may be placed into a 2-8°C refrigerator for up to 24 hours.
- 8) Following this, experiments to measure KRT9 expression and histology will begin.

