4.1.1 BLINDING/RANDOMIZATION

The clinicians will not be blinded, but the research staff who measure epidermal thickness and KRT9 levels will be blinded. It will be impossible to blind the clinicians since they will be injecting the cells versus vehicle. Although we could blind the clinicians to the identity of volar versus non-volar cells, it might be important to judge adverse events and will not impact on endpoint determination—primarily occurring in the laboratory. Another reason not to blind the clinicians is that this is a feasibility trial.

We will blind the research staff by labeling sites/biopsies with numbers (1, 2 or 3) rather than the identity of injected cells at that location. At the injection visit, the numbers are assigned as in the CRF (see Appendix V) with the corresponding identity of cells injected by the clinician. This injection form will not be available to research staff unless there is an adverse event when un-blinding will occur. Blinding will occur for research staff both during measurements of epidermal thickness/area by OCT as well as in the laboratory phase where the removed injection sites will be analyzed by histology and RT-PCR.

The subjects will also only be told the number of each site so that subjects will be blinded as well (See Appendix VI; injection diary).

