5.2.5.6 GRAFT REMOVAL VISIT (VISIT #12) (STUDY DAY 182 +/-7 DAYS)

At this visit, the study team will obtain:

- Vital signs including HR, RR and BP
- Clinical photographs of the injection sites
- Thickness measurements/Area of epidermal thickness via Optical Coherence Tomography (OCT)
- Skin induration measurement via SkinFibroMeter
- AE assessment/symptom diary review
- Graft removal will be performed as was the initial biopsy and is detailed in Appendix VII.

5.2.6 SUTURE REMOVAL VISIT (VISIT #13) (STUDY DAY 196 +/- 7 DAYS OR 14 DAYS +/-2 AFTER EARLY GRAFT REMOVAL)

All participants with the exception of those who undergo early graft removal will return for suture removal at this time point. “Early graft removal” participants will return to have sutures removed 14 days (+/- 2 days) after their graft removal. “Early graft removal” subjects will have fewer graft monitoring visits, but will be expected to return for a final evaluation visit (see Visit 11).

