9.2.2 SECONDARY OUTCOME VARIABLES

Secondary outcome variables for this study will be 1) an increase in epidermal thickness as detected by optical coherence tomography in vivo, or by histology, and 2) an increase in KRT9 by RT-PCR, western or immunohistochemistry

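### Appendix VII prints the injected material on each excised-site tube, contradicting the number-only labelling on which Section 4.1.1 bases the laboratory blind.

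*Combined protocol and SAP*

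**What the plan says.** Section 4.1.1 leaves the clinicians unblinded and blinds the staff who measure epidermal thickness and KRT9. The method is stated: "We will blind the research staff by labeling sites/biopsies with numbers (1, 2 or 3) rather than the identity of injected cells". It covers OCT measurement, "as well as in the laboratory phase where the removed injection sites will be analyzed by histology and RT-PCR". The record that links number to cell type is kept from these staff: "This injection form will not be available to research staff unless there is an adverse event when un-blinding will occur".

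Section 5.2.5.6 sends the reader to an appendix for the excision itself: "Graft removal will be performed as was the initial biopsy and is detailed in Appendix VII". Step 5 of that appendix bisects each specimen between two preservatives and sets the label: "Labeling of tubes will include the subject initials, unique participant ID, the date, the injection #, and the identity (vehicle, volar or nonvolar". Step 6 continues "The biopsies will be directly hand delivered to the" receiving laboratory (its name is removed), and step 8 reads "Following this, experiments to measure KRT9 expression and histology will begin".

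Section 9.2.2 lists two secondary outcomes. The first is "an increase in epidermal thickness as detected by optical coherence tomography in vivo, or by histology"; the second is an increase in KRT9 by RT-PCR, western or immunohistochemistry.

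**The concern.** The two sections give opposite labelling instructions for the same specimens and the same assays. Because Appendix VII puts number and identity on one label, the tube shows the link that Section 4.1.1 withholds by keeping the injection form from research staff.

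Section 4.1.1 defends the unblinded clinicians partly on the ground that the endpoints are determined mainly in the laboratory. That defence is only as good as the laboratory blind. At stake is protection against reader bias when volar, non-volar and vehicle sites are compared on excised tissue, which is the material for secondary objective 2 (molecular change) and for the histological part of the thickness outcome.

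**Working it through.** The plan states no figure on this point, so the check is a comparison of the texts.

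1. **Same specimens?** Yes. The heading of Appendix VII calls them baseline biopsies, but its body describes excision of the 3 injection sites, its label has a vehicle category that no baseline biopsy could have, and Section 5.2.5.6 cites it for graft removal.

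2. **Same assays?** Yes. Section 4.1.1 names histology and RT-PCR on the removed sites; Appendix VII step 8 names KRT9 expression and histology.

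3. **Can both instructions hold?** No. Section 4.1.1 replaces identity with a number; Appendix VII prints the number and the identity together.

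4. **Is there a masking step in between?** None is described. Steps 6 and 7 cover delivery, then immediate processing or refrigeration; step 8 starts the assays.

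5. **Is Appendix III in conflict too?** No. It also puts volar or non-volar on tubes, but those hold the harvest biopsies that go to the cell laboratory for culture, not to outcome readers.

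6. **How far does it reach?** Each participant has 3 sites, each bisected, so 3 × 2 = 6 halves come from tubes labelled this way. This counts material and does not measure bias. By read-out:

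| Read-out | Uses excised tissue | Exposure to reader judgement |
|---|---|---|
| Histological thickness | yes | more |
| Immunohistochemistry, western | yes | more |
| RT-PCR for KRT9 | yes | less |
| OCT thickness | no, read in vivo before excision | not directly affected |
| Tolerability (primary) | no | not affected |

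7. **Which planned tests depend on it?** Section 9.2 names two end-of-study t-tests. The KRT9 mRNA test rests wholly on excised tissue. The epidermal thickness test does so only if histology supplies the values; secondary objective 1 speaks of non-invasive measurement, which points to OCT.

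**The case against.** The strongest reply concedes the conflict and disputes its weight.

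- **Narrow effect.** The only named test that rests wholly on excised tissue uses RT-PCR, the read-out least open to judgement. The judgement-based reads have no named significance test unless histology supplies the thickness values. All affected outcomes are secondary, in an open-label feasibility study. This stands, and it limits the importance of the point.

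- **Possible carry-over.** Step 5 closely follows the wording of Appendix III, and the heading seems to have been carried across with it. Section 4.1.1 remains the explicit statement of intent. This is plausible, but it explains the conflict without removing it: staff who follow the removal procedure will write the identity on the tube.

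- **Unblinding not shown.** A reader might infer that every laboratory reader sees the identity, or that the results will be biased. The documents do not support that. They do not say that those who receive tubes also read outcomes, and silence on recoding does not prove that none takes place. What is established is that the stated method is contradicted.

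- **Spill-over to OCT.** A reader might also infer that a number printed beside an identity compromises the OCT blind. The schedules in the appendices excise the 3 sites together, so no later OCT visit measures those sites in that participant. OCT reads in other participants would be exposed only if the number-to-cell mapping were constant or predictable, and the documents do not say whether it is.

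- **Deleting the phrase may not be enough.** Section 4.1.1 has randomization in its heading but describes no random or varying assignment of the numbers 1 to 3. With a constant mapping, readers could infer identity from the number alone. This objection stands and shapes the fix.

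**Conclusion.** The contradiction is real and should be corrected. As written, Appendix VII departs from the labelling method by which Section 4.1.1 blinds the laboratory, for every excised injection site.

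The consequence is limited to tissue-based secondary read-outs, most of all histology, immunohistochemistry and western. The primary tolerability outcome and in-vivo OCT are not directly affected. No change in false-positive rate can be stated, because the documents give no size for reader bias.

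The conclusion assumes that no recoding procedure exists outside the text available; none is mentioned in it. If one exists, writing it into Appendix VII would meet much of the concern, but the two passages would still need to be reconciled.

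**What to change.** 1. **Appendix VII, step 5.** Delete the last item of the label, the identity of the injected material. Keep the rest: initials, participant ID, date and injection number. Leave Appendix III as it is.

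2. **Section 4.1.1.** Add a sentence on custody of the key. It stays with the injecting clinician or another person who reads no outcomes, and is withheld from laboratory readers until all laboratory readings are recorded, apart from the adverse-event unblinding already provided. The repeated comparisons in Section 9.2 can still be run, because the key holder can group the values. Do not release the key participant by participant: that would loosen the present rule, show accumulating results to the readers, and unblind later participants if the mapping is constant.

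3. **Check traceability before shortening the label.** Section 4.1.1 says the form in Appendix V records identity, but the form as it appears has a site number, location, vial number, times and cell dose, and no column for identity. Confirm that the site number leads through the vial number to the material injected. Include Phase Two, where a site may receive up to 4 administrations with different contents; make clear there that the injection number on the tube means the site and not the order of administration.

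4. **Check the assignment.** Confirm that the assignment of numbers 1 to 3 to volar, non-volar and vehicle varies between participants, and say so in Section 4.1.1.

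The cost is one deleted phrase, a short addition to Section 4.1.1 and two checks, with no new visits, samples or assays. If a check fails, the administration form or the way numbers are assigned would also need amending; deleting the phrase would not then be enough to restore the blind.
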